### **10.10.5 Stratification**

Randomisation will be stratified by country, anatomical location (face or scalp) and history of SCC (none or previous SCC). Three countries are identified with a total of 48 investigational sites. Roughly 10 subjects will be enrolled at each site.

---

## 10.10.6 Safety Analysis

### 10.10.6.1 Analysis of Primary and Secondary Safety Endpoints

The primary endpoint and secondary safety endpoint are listed in sections [10.9.1](#) and [10.9.2](#) respectively. Both endpoints will follow the same method of analysis.

The 3-year cumulative incidence will be calculated for each treatment group using methods of survival analysis for estimation of cumulative incidence in the presence of censored time-to-event data. Annual incidence rates will also be presented for each group. The cumulative incidence rates will be presented for the event of SCC as primary endpoint and for SCC and other neoplasia as secondary. No formal statistical test comparing the two arms will be performed. For descriptive purposes, as an additional analysis, the difference in cumulative incidence rates between the two arms will be estimated and presented together with its 95% confidence interval.

A landmark analysis, conditional on patients' responses at Week 20, will additionally be performed in order to exclude SCC and other neoplasia reported within the first 20 weeks which are not assumed to be associated with the study treatment. Patients who experience a neoplasia before the 20-week landmark time point are excluded from the time-to-event analysis, which is otherwise conducted as above.

### 10.10.6.2 Adverse Events

Reporting of adverse events will be based on the Safety Analysis Set.

All adverse events recorded will be reported in listings. The investigator's verbatim term of each adverse event will be mapped to SOC and preferred terms using the current version of the Medical Dictionary for Regulatory Activities (MedDRA) thesaurus.

An overall summary of the number (percentage) of subjects with any treatment emergent adverse events (TEAEs), SAEs, premature discontinuations from treatment or from the trial due to adverse events, treatment related AEs, LSRs, severe AEs (maximum intensity indicated as severe in the CRF) will be presented. The overall and treatment related AE summary will also be presented by trial period of the start date of AEs: until Week 20, from Week 20 until Month 12, Month 12 to 24, Month 24 to 36).

The number and percent of subjects with AEs will be tabulated by body system and preferred term for the above summaries. Within a specific body system or preferred term, the subject will be counted only once if more than one event is reported. Summaries will be presented by decreasing frequency.

Listings will be provided for all subjects with SAEs and study discontinuations due to adverse events.

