3.1 List of Abbreviations

AE	Adverse Event
AK	Actinic Keratosis
ATC	Anatomical Therapeutic Chemical
BCC	Basal Cell Carcinoma
CCTP	Consolidated Clinical Trial Protocol
CI	Confidence Interval
CM	Concomitant Medication
DK	Denmark
FAS	Full Analysis Set
ICH	International Conference on Harmonisation
LSR	Local Skin Response
MedDRA	Medical Dictionary for Regulatory Activities
PP	Per Protocol
PT	Preferred Term
SCC	Squamous Cell Carcinoma
SD	Standard Deviation
SE	Standard Error
SMQ	Standardised MedDRA Query
SOC	System Organ Class
WHODD	WHO Drug Dictionary

4 Statistical Analysis Plan Authors

PPD [REDACTED], M.Sc., Principal Statistician, Biostata Aps, [name], tel: PPD [REDACTED], e-mail: PPD [REDACTED]

PPD [REDACTED], PhLic, Senior Clinical Project Manager, Trial Execution, LEO Pharma A/S, [name], tel: PPD [REDACTED], e-mail: PPD [REDACTED]

PPD [REDACTED]; MS, PhD (cand), Senior Medical Writer, Pharma IT, [name]; tel: PPD [REDACTED], e-mail: PPD [REDACTED]

PPD [REDACTED], MD, PhD, Associate Research Fellow, Medical Department, LEO Pharma A/S, [name], tel: PPD [REDACTED], e-mail: PPD [REDACTED]

5 Introduction

The statistical analysis will be performed as outlined in the Consolidated Clinical Trial Protocol (CCTP). This Statistical Analysis Plan contains a more technical and detailed elaboration of some points in the statistical analysis section in the CCTP.

6 Trial Analysis Sets

The full analysis set (FAS) is defined as all randomised subjects.

The safety analysis set is defined as all subjects who receive an initial study treatment and have safety data available.

The per protocol (PP) analysis set will be used as safety and efficacy subsets and is defined as subjects in the FAS who complete the trial without major protocol deviations affecting the primary and secondary safety and efficacy endpoints. Censoring as well as a full exclusion from the PP analysis set will be used in the primary analysis and in all other time-to-event analyses. A subject who is to be excluded from the PP analysis set will be in the analysis until the subject is censored at the time the event leading to exclusion from PP occurs in time-to-event analyses in case the event occurs after Day 1. This is in line with estimands defined by the composite strategy in ICH E9 (R1) addendum on estimands (1).

Please see the Analysis Set Definition Document for details.

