7.3.5 Adverse Events

Adverse events (AEs) will be presented as described in the CCTP.

Trial ID: LP0041-63	Date: 28-AUG-2019	Version: Final 1.0 Page 12 of 32
---------------------	--------------------------	-------------------------------------

An AE will be considered treatment emergent if the event emerges during treatment having been absent pre-treatment or worsens relative to the pre-treatment state. This is as defined in ICH E9.

Skin malignancies inside the treatment area are defined using Medical Dictionary for Regulatory Activities (MedDRA) v 15.1 as AEs from the Standardised MedDRA Query (SMQ) *skin malignant tumours*. Skin malignancies inside the treatment area will be presented by PT.

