- Table 2-8 Annual incidence of SCC in the treatment area: per protocol analysis set [[Shell 6](#)]
- Table 2-9 Summary of SCC in the treatment area from baseline to end of trial: safety analysis set [[Shell 7](#)]
- Table 2-10 Summary of SCC in the treatment area from baseline to end of trial: per protocol analysis set [[Shell 7](#)]
- Table 2-11 Annual incidence of SCC and other neoplasia in the treatment area: safety analysis set [[Shell 6](#)]
- Table 2-12 Annual incidence of SCC and other neoplasia in the treatment area: per protocol analysis set [[Shell 6](#)]
- Table 2-13 Incidence of SCC in the treatment area by subgroups: safety analysis set [[Shell 8](#)]
- Table 2-14 Incidence of SCC in the treatment area by subgroups: per protocol analysis set [[Shell 8](#)]
- Table 2-15 Incidence of SCC and other neoplasia in the treatment area by subgroups: safety analysis set [[Shell 8](#)]
- Table 2-16 Incidence of SCC and other neoplasia in the treatment area by subgroups: per protocol analysis set [[Shell 8](#)]
- Table 2-17 Incidence of SCC and other neoplasia in the treatment area from week 20 to month 36: safety analysis set [[Shell 5](#)]

Trial ID: LP0041-63	Date: 28-AUG-2019	Version: Final 1.0 Page 19 of 32
---------------------	--------------------------	-------------------------------------

Table 2-18 Incidence of SCC and other neoplasia in the treatment area from week 20 to month 36: per protocol analysis set [[Shell 5](#)]

Table 2-19 Difference in the incidence of SCC in the treatment area: safety analysis set [[Shell 9](#)]

Table 2-20 Difference in the incidence of SCC in the treatment area: per protocol analysis set [[Shell 9](#)]

Table 2-21 Difference in the incidence of SCC and other neoplasia in the treatment area: safety analysis set [[Shell 9](#)]

Table 2-22 Difference in the incidence of SCC and other neoplasia in the treatment area: per protocol analysis set [[Shell 9](#)]

Adverse events

Table 2-23 Overall summary of adverse events from start of treatment to end of trial: safety analysis set

Table 2-24 Overall summary of adverse events from start of treatment to Week 20: safety analysis set

Table 2-25 Overall summary of adverse events from Week 20 to end of trial: safety analysis set

Table 2-26 Overall summary of adverse events by period: safety analysis set

Table 2-27 Adverse events from start of treatment to Week 20 by SOC: safety analysis set

Table 2-28 Adverse events by SOC: safety analysis set

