Table 2-29 Adverse events from start of treatment to Week 20 by SOC and PT: safety analysis set

Table 2-30 Adverse events from Week 20 to end of trial by SOC and PT: safety analysis set

Table 2-31 Frequent adverse events ($\geq 5\%$ in any treatment group) from start of treatment to Week 20 by SOC and PT: safety analysis set

Table 2-32 Frequent adverse events ($\geq 5\%$ in any treatment group) from Week 20 to end of trial by SOC and PT: safety analysis set

Table 2-33 Adverse events from start of treatment to Week 20 by severity, SOC, and PT: safety analysis set

Table 2-34 Adverse events from Week 20 to end of trial by severity, SOC, and PT: safety analysis set

Table 2-35 Related adverse events from start of treatment to Week 20 by SOC and PT: safety analysis set

Table 2-36 Related adverse events from Week 20 to end of trial by SOC and PT: safety analysis set

Trial ID: LP0041-63	Date: 28-AUG-2019	Version: Final 1.0 Page 20 of 32
---------------------	--------------------------	-------------------------------------

Table 2-37 Related adverse events from start of treatment to Week 20 by severity, SOC, and PT: safety analysis set

Table 2-38 Related adverse events from Week 20 to end of trial by severity, SOC, and PT: safety analysis set

Table 2-39 Related adverse events by period, SOC, and PT: safety analysis set

Table 2-40 Adverse events from start of treatment to Week 20 by causal relationship, SOC, and PT: safety analysis set

Table 2-41 Adverse events from Week 20 to end of trial by causal relationship, SOC, and PT: safety analysis set

Table 2-42 Serious adverse events from start of treatment to Week 20 by SOC and PT: safety analysis set

Table 2-43 Serious adverse events by SOC and PT: safety analysis set

Table 2-44 Serious adverse events from start of treatment to Week 20 by causal relationship, SOC, and PT: safety analysis set

Table 2-45 Serious adverse events from Week 20 to end of trial by causal relationship, SOC, and PT: safety analysis set

Table 2-46 Skin malignancies inside treatment area by PT: safety analysis set

Table 2-47 Skin malignancies outside treatment area by PT: safety analysis set

Table 2-48 Adverse events leading to withdrawal from trial by SOC and PT: safety analysis set

Table 2-49 Adverse events from start of treatment to Week 20 by outcome: safety analysis set

Table 2-50 Adverse events from Week 20 to end of trial by outcome: safety analysis set

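### By-period adverse event percentages cannot be compared across periods: the periods run about 20, 32, 52 and 52 weeks, and no at-risk number or subject-time is planned

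*Protocol*

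**What the plan says.** Protocol section 10.10.6.2 sets the population: "Reporting of adverse events will be based on the Safety Analysis Set". The measure is a count and percentage of subjects: "An overall summary of the number (percentage) of subjects with any treatment emergent adverse events (TEAEs" and other categories. It then adds a split by period: "The overall and treatment related AE summary will also be presented by trial period of the start date of AEs". The periods are "until Week 20, from Week 20 until Month 12, Month 12 to 24, Month 24 to 36".

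SAP section 6 defines the safety set as "all subjects who receive an initial study treatment and have safety data available". Membership is therefore settled at the start and does not shrink when a subject leaves. Under Protocol section 10.5, withdrawn subjects are not replaced.

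SAP section 7.3.5 adds nothing on denominators or exposure: "Adverse events (AEs) will be presented as described in the CCTP". SAP Appendix I lists Table 2-26, "Overall summary of adverse events by period: safety analysis set", and Table 2-39, "Related adverse events by period, SOC, and PT: safety analysis set". It also lists tables running from Week 20 to the end of the trial, among them 2-25, 2-30, 2-32 and 2-36. Appendix II has no shell for any of these.

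The recording rule changes at Week 20 (Protocol section 10.7.5.1, Tables 2 and 3). Inside the treatment area all AEs are recorded throughout, and BCC and SCC are recorded throughout at any location. Outside the area, every other AE is recorded until Week 20, but afterwards only treatment-related serious ones.

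**The concern.** A reader will naturally use a by-period table to see whether events persist or fade after treatment, although the protocol gives no purpose for the split. Three features stand in the way, and they do not all pull in the same direction:

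- The longest period is 2.6 times the shortest, so a longer period collects more subjects with an event at the same risk.
- A subject who left before Month 24 cannot have an event recorded in Months 24 to 36. If that subject stays in the denominator, the late percentage is too low.
- Fewer kinds of event are recorded after Week 20, which lowers later figures again for all AEs and for related AEs.

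A percentage that mixes these cannot show the time course. If one arm loses more subjects than the other, its late percentages fall for that reason alone.

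**Working it through.** The plan gives no AE rate and no drop-out rate, so there is no stated figure to reproduce. The period lengths come from the plan; every rate below is an assumption.

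**Period lengths.** Week 20 is 20 × 7 / 365.25 = 0.383 years. The periods are therefore 0.383, 0.617, 1 and 1 years, or 20.0, 32.2, 52.2 and 52.2 weeks. The ratio is 1 : 1.61 : 2.61 : 2.61.

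**Length alone.** With a constant rate λ and no drop-out, the percentage with an event in a period of length L is 1 − exp(−λL). At λ = 0.2 per subject-year:

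- Until Week 20: 1 − exp(−0.0767) = 7.4%
- Week 20 to Month 12: 1 − exp(−0.1233) = 11.6%
- Each 12-month period: 1 − exp(−0.2) = 18.1%

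**Length and drop-out together.** With a constant drop-out hazard c, the percentage of the whole safety set with an event in the period from a to b is

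exp(−ca) × λ/(λ+c) × [1 − exp(−(λ+c)(b−a))].

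For 20% drop-out over three years, c = −ln(0.8)/3 = 0.0744.

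| Denominator (λ = 0.2) | To Week 20 | Week 20 to Month 12 | Month 12 to 24 | Month 24 to 36 |
|---|---|---|---|---|
| Whole set, no drop-out | 7.4% | 11.6% | 18.1% | 18.1% |
| Whole set, 20% drop-out | 7.3% | 11.0% | 16.2% | 15.1% |
| In trial at period start, 20% drop-out | 7.3% | 11.3% | 17.5% | 17.5% |

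The third row is the second divided by exp(−ca), which is 1, 0.972, 0.928 and 0.862.

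The rise is there in full without drop-out, so it comes from period length. Drop-out appears as a fall between the two equal periods, from 16.2% to 15.1%. The at-risk denominator removes that fall but leaves the rise.

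**Size of the drop-out effect.** The share of Month 24 to 36 time actually observed is [exp(−2c) − exp(−3c)]/c. It is 0.90, 0.87, 0.83 and 0.74 at three-year drop-out of 12, 15, 20 and 30%.

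**Between arms.** With the same λ = 0.2 in both arms and drop-out of 10% against 30%, the Month 24 to 36 percentages of the whole set are 16.6% and 13.5%.

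**Which rate removes the length effect.** Divide subjects with a first event in the period by subject-time that ends at that event, at leaving, or at the end of the period. Expected events are exp(−ca) × λ/(λ+c) × [1 − exp(−(λ+c)L)], and expected time is the same expression without λ. The ratio is λ, or 20.0 per 100 subject-years, in every period and at any drop-out. If time instead runs on past the event, the no-drop-out figures are 7.38/0.383 = 19.3, 11.60/0.617 = 18.8, and 18.1 for each 12-month period. That is close to constant, but not exactly so.

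**The case against.** The strongest reply has four parts.

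1. **The denominator is not written out.** The documents name an analysis set; they do not state a denominator for each period. This is right. The whole-set reading is the natural one from the table titles, but it is an inference.
2. **The all-AE table cannot follow a constant-risk pattern.** Recording narrows sharply after Week 20, so the overall table may well fall. This is also right, and it limits the illustration to events recorded alike throughout: those inside the treatment area, and BCC and SCC. It does not make the percentages comparable; it is one more reason why they are not.
3. **Much can be reconstructed.** Shell 6 prints subject-years to Months 12, 24 and 36, SAP Table 1-4 gives withdrawals by last visit attended, and all AEs are listed. This stands in part. Subtracting the Shell 6 totals gives approximate time for the last two periods, but its first cut is Month 12, so the first year cannot be split at Week 20.
4. **Little depends on it.** Both arms share the periods, so length affects them alike, and a difference between arms arises only if drop-out differs. The documents give no drop-out figure, and no test is attached to these tables. This stands and sets the weight of the point.

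A reader might also infer that leavers in the denominator cause the apparent rise. They do not: they lower the later percentages and partly offset it.

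**Conclusion.** The point holds as a minor one about presentation. Percentages over periods of 20, 32, 52 and 52 weeks, without an at-risk number or subject-time, do not show the time course of AEs. At an assumed 0.2 first events per subject-year, period length alone takes a constant risk from 7.4% to 18.1%. If leavers stay in the denominator, an assumed 20% three-year drop-out separately lowers the last period from 16.2% to 15.1%. These figures rest on constant event and drop-out hazards and on uniform recording.

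Two stronger readings are not supported. One is that the all-AE or related-AE tables will show a spurious rise. The recording change pulls them down, so the net direction is unknown. The other is that the trial's main safety result is affected. SCC and other neoplasia are analysed by Kaplan-Meier with censoring (SAP sections 7.3.1 to 7.3.3), and Shells 6 and 7 already provide subject-years and a rate per 100 patient-years. The by-period AE tables merely lack what the SAP uses elsewhere.

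**What to change.** In SAP Tables 2-26 and 2-39, and in the tables that start at Week 20:

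- Print the number of safety-set subjects still in the trial at the start of the period, and use it as the denominator.
- Add observed subject-years in the period, and subjects with a first event in that period per 100 subject-years. For this rate, end each subject's time at the first event in the period, at the last visit, or at the end of the period, whichever comes first. This column removes the length effect; the at-risk denominator alone does not.
- Restrict any comparison across Week 20 to events recorded the same way throughout (inside the treatment area, and BCC and SCC), and footnote the recording change.

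Applying the 5% cut in Table 2-32 to the at-risk number is optional, since that table covers one period.

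The cost is a short SAP addition and minor programming from event and visit dates already held. The drawback is a few extra columns and denominators that differ between periods. The primary endpoint is untouched.

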### 10.10.6.3 Local Skin Responses

The incidence and grade of LSRs will be summarised by treatment arm at each assessment visit by anatomical location based on the Safety Analysis Set. Local skin response grades will be summarised by frequency counts and descriptive statistics by treatment arm and visit for each of the six individual LSRs: erythema, flaking/scaling, crusting, swelling, vesiculation/pustulation, and erosion/ulceration.

A composite (sum) score will be obtained by summing the six individual LSR scores at each visit. The composite score and change from baseline will be summarized by treatment arm at each visit using descriptive statistics. The visit of occurrence of maximal intensity will be tabulated.

Local skin responses will be converted into MedDRA preferred terms applying the following conversions seen in [Table 4](#). These adverse events will be reported separately from adverse events recorded on the adverse event form in the CRF.

Table 4: Conversion of LSRs to MedDRA Preferred Terms

LSR Term	LSR Grade	MedDRA Preferred Term
Erythema	1-4	Application site erythema
Flaking/Scaling	1-4	Application site exfoliation.
Crusting	1-4	Application site scab
Swelling	1-4	Application site swelling
Vesiculation/Pustulation	1	Application site vesicles
	2-4	Application site pustules
Erosion/Ulceration	1-3	Application site erosion
	4	Application site ulcer

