## 8.1 ACTINIC KERATOSIS

Actinic keratosis is a common skin condition visible as thickened, cornified, scaly lesions and characterised histologically by atypical epithelial proliferation (24). Actinic keratoses usually develop on areas that are frequently exposed to the sun (e.g., face, ears, scalp, neck, forearms, and back of the hands). Patients with AK often express embarrassment, worry, and irritation related to the change in appearance of their skin and unsightly nature of the lesions (25, 26). In addition to the emotional strain, AK lesions can be painful and easily traumatised causing bleeding (26, 27, 28, 29).

In population studies performed in the EU and US, reported prevalence rates for AK have been approximately 11-25% of the population, while estimates are higher in Australian studies (up to 60%) (24). Patients with AK tend to have Fitzpatrick type I or II skin (fair skin) which burns with sun exposure and does not tan (28).

In the context of AK, the skin of patients with AKs shows field cancerisation, characterised by the epithelial surface of the photodamaged area being susceptible to the development of additional AKs or a malignancy. This is evidenced by the presence of multiple subclinical and clinically visible AK lesions as well as multifocal preneoplastic changes with genetic mutations (30). There is also increasing evidence that AK represents SCC in situ in its earliest stages (15, 24, 31). Histological evidence shows that contiguous AK is present in 97% of SCC lesions on sun-damaged skin (15). Actinic keratosis is linked epidemiologically to development of SCC (1), and both conditions share specific gene expression (2). If left untreated, AK may regress, or alternatively, may progress to SCC, with significant morbidity and possible lethal outcome (15).

Predicting which AKs may progress to SCC is not possible, nor is the conversion rate for an AK to SCC clear: the transformation rate from an AK lesion to SCC within one year has been reported to be <1:1000 (32). Further mathematical modelling of these data has predicted that for an individual with an average of 7.7 AKs, the probability of at least one transforming within a 10-year period is approximately 10% (33).

Diagnosis of AKs is based upon the clinical presentation (23). When there is doubt as to the clinical differentiation between AKs and SCCs, histological confirmation may be necessary (23).

---

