#### **10.6.6.1 Ingenol Mebutate**

##### ***Skin Exposure***

The most common LSRs reported in the AK studies were erythema, flaking/scaling, and crusting. Less common LSRs included swelling/edema, vesiculation/pustulation, and erosion/ulceration. The mean maximum composite LSR score for patients treated with ingenol mebutate gel, 0.015% was 9.1 (SD, 4.1) compared with 1.8 (SD, 1.6) for patients treated with vehicle, with the majority of patients having a maximum score on Day 4 and return to baseline by Day 29.

Studies in healthy volunteers showed no evidence of skin sensitisation, phototoxicity, or photosensitisation following the application of ingenol mebutate gel.

---

Investigators conducting clinical trials with ingenol mebutate gel should ensure that investigational site staff and subjects are trained in the protocol-specified application procedure(s) and follow appropriate precautions. Investigators must monitor their subjects for the emergence and resolution of LSRs and AEs.

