## **Appendix III**

### Local Skin Response Grading Scale

# Local Skin Response Grading Scale

Treatment area(s) to be assessed using the following categories and grading scale

Grade	0	1	2	3	4
Erythema	 Not present	 Slightly pink <50%	 Pink or light red >50%	 Red, restricted to treatment area	 Red extending outside treatment area
Flaking/Scaling	 Not present	 Isolated scale, specific to lesions	 Scale <50%	 Scale >50%	 Scaling extending outside treatment area
Crusting	 Not present	 Isolated crusting	 Crusting <50%	 Crusting >50%	 Crusting extending outside treatment area

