Table 2-51 Conversion of LSRs to MedDRA by SOC and PT: safety analysis set

LSRs

Table 2-52 – 2-57: Frequency of LSR component <component> by visit: safety analysis set

Table 2-58 – 2-63: Frequency of LSR component <component> by anatomical location and visit: safety analysis set

Table 2-64 Composite LSR score by visit: safety analysis set

Table 2-65 Composite LSR score by anatomical location and visit: safety analysis set

Table 2-66 Change in composite LSR score from baseline by visit: safety analysis set

Table 2-67 Summary of visits of maximum post baseline composite LSR score: safety analysis set

Table 2-68 Maximum post baseline LSR score by LSR component: safety analysis set

Table 2-69 Maximum post baseline composite LSR score: safety analysis set

Other safety endpoints

Table 2-70 Physical examination by visit: safety analysis set

Figures

Figure 2-1 Time to SCC: safety analysis set [[Shell 10](#)]

Figure 2-2 Time to SCC: per protocol analysis set [[Shell 10](#)]

Figure 2-3 Time to SCC or other neoplasia: safety analysis set [[Shell 10](#)]

Figure 2-4 Time to SCC or other neoplasia: per protocol analysis set [[Shell 10](#)]

Figure 2-5 Composite LSR score mean profile by visit: safety analysis set

Figure 2-6 LSR components by visit: safety analysis set

Tables and Figures, Efficacy Data (Module 4)

Tables

Table 3-1 Complete clearance by visit: full analysis set [[Shell 11](#)]

Table 3-2 Complete clearance by visit: per protocol analysis set [[Shell 11](#)]

Table 3-3 Analysis of complete clearance after the last treatment cycle: full analysis set [[Shell 12](#)]

Table 3-4 Analysis of complete clearance after the last treatment cycle: per protocol analysis set [[Shell 12](#)]

Table 3-5 Analysis of complete clearance at Month 12: full analysis set [[Shell 12](#)]

Table 3-6 Analysis of complete clearance at Month 12: per protocol analysis set [[Shell 12](#)]

Table 3-7 Partial clearance by visit: full analysis set [[Shell 11](#)]

Table 3-8 Partial clearance by visit: per protocol analysis set [[Shell 11](#)]

Table 3-9 Analysis of partial clearance after the last treatment cycle: full analysis set [[Shell 12](#)]

Table 3-10 Analysis of partial clearance after the last treatment cycle: per protocol analysis set [[Shell 12](#)]

Table 3-11 Analysis of partial clearance at Month 12: full analysis set [[Shell 12](#)]

Table 3-12 Analysis of partial clearance at Month 12: per protocol analysis set [[Shell 12](#)]

Figures

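### Local skin responses of grade 1 or more are coded as application-site adverse events without reference to the Day 1 pre-dose grade, which can overstate any-grade incidence and dilute the between-arm difference in one descriptive table (SAP Table 2-51)

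*Protocol*

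**What the plan says.** Protocol 10.10.6.3 sets the rule: "Local skin responses will be converted into MedDRA preferred terms applying the following conversions". In Table 4 each of the six LSR components receives a MedDRA preferred term from grade 1 upwards. Flaking/scaling of grades 1 to 4 becomes "Application site exfoliation". The section then treats the results as adverse events in their own right: "These adverse events will be reported separately from adverse events recorded on the adverse event form in the CRF". It does not mention the pre-dose grade and does not say which visits feed the conversion.

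SAP 7.3.6 adds no rule of its own and refers back to the protocol. The output is SAP Table 2-51, titled "Conversion of LSRs to MedDRA by SOC and PT: safety analysis set"; no shell is given for it.

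A pre-dose grade exists. Under Protocol 10.1.3, Visit 2, LSRs are assessed before randomisation and the first application, and SAP 7.1 defines baseline as the last assessment before dosing.

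For adverse events in general, SAP 7.3.5 counts an event as treatment emergent if it was not there before treatment or "worsens relative to the pre-treatment state".

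**The concern.** The lowest scaling grade in Protocol Appendix III is "Isolated scale, specific to lesions". Protocol 8.1 describes actinic keratoses (AKs) as "visible as thickened, cornified, scaly lesions", and inclusion criterion 2 requires 5 to 9 of them in the treatment area. An untreated lesion can therefore score grade 1 before any drug is applied. If it still scores grade 1 at a later visit, Table 4 read literally produces an application-site event although nothing has changed.

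This matters because LSRs are a main feature of the safety profile of ingenol mebutate (Protocol 8.2.1), and comparing them between the products is a stated aim (Protocol 8.3). LSRs that fit the grading scale are kept off the adverse event form unless they are serious (Protocol 10.7.5.1 and 10.7.6.1), so Table 2-51 is essentially their only MedDRA-coded summary. Background scale counted in both arms raises both percentages and draws them together.

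**Working it through.** The plan gives no figure for converted LSRs, so there is none to reproduce. The check has two parts.

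**1. Is a baseline condition stated anywhere?**

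- Protocol 10.10.6.3, Table 4: conversion by grade alone, from grade 1.
- SAP 7.3.6: refers back to the protocol.
- SAP Table 2-51: the title has no limit, whereas the titles of Tables 2-66 to 2-69 refer either to change from baseline or to the period after it.
- SAP 7.3.5: has the wanted condition but does not say that it covers converted LSRs.

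So no condition is attached, and two programmers could produce different versions of Table 2-51 from the same text.

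**2. What would the omission do to the table?**

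Inputs, all assumed because the documents give none of them:

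- b: share of subjects with a grade of 1 or more at Day 1, taken as equal in the two arms;
- p: share with a new or worse response after dosing (pA and pB in the two arms), taken as independent of b.

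Subjects with a Day 1 grade are taken as counted, as the literal rule allows. Then:

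- any-grade incidence = 1 − (1 − b)(1 − p)
- excess over p = b(1 − p)
- between-arm difference = (1 − b)(pA − pB)

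With pA = 0.90 and pB = 0.70, a true difference of 20 points:

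| b | Arm with more reaction | Arm with less reaction | Difference shown |
|---|---|---|---|
| 0 | 90% | 70% | 20 points |
| 0.2 | 1 − 0.8 × 0.1 = 92% | 1 − 0.8 × 0.3 = 76% | 16 points |
| 0.4 | 1 − 0.6 × 0.1 = 94% | 1 − 0.6 × 0.3 = 82% | 12 points |
| 0.6 | 1 − 0.4 × 0.1 = 96% | 1 − 0.4 × 0.3 = 88% | 8 points |
| 0.8 | 1 − 0.2 × 0.1 = 98% | 1 − 0.2 × 0.3 = 94% | 4 points |

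At b = 0.8 the excess is 0.8 × 0.1 = 8 points in the first arm and 0.8 × 0.3 = 24 points in the second. The arm with less true reaction is inflated more, which is why the gap narrows.

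The proportional shrinkage does not depend on the assumed rates. With 60% against 40%, the difference is again 16 points at b = 0.2 (68% against 52%) and 4 points at b = 0.8 (92% against 88%).

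**Can b be read from the protocol?** No. The section on skin exposure (10.6.6.1) gives a mean maximum composite score of 9.1 on ingenol mebutate "compared with 1.8 (SD, 1.6) for patients treated with vehicle". The vehicle value is a maximum over visits, summed over six components, after vehicle was applied. It is neither a pre-dose score nor a scaling score.

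**The case against.** A reader might infer that the conversion hides the difference between the products. The documents do not support that. SAP Appendix I also plans grade frequencies for each component by visit (Tables 2-52 to 2-57) and by location and visit (2-58 to 2-63), the composite score and its change from baseline (2-64 to 2-66), and post-baseline maxima (2-67 to 2-69). A contrast in graded responses would still be visible there. The converted events are also kept apart from those on the adverse event form.

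A reader might also infer that unchanged scale will certainly be counted, or that the SAP contradicts itself. Neither is established. The protocol calls converted LSRs adverse events, so SAP 7.3.5 could be read to govern them, which would supply the missing condition. If it does not govern them, Table 2-51 makes no claim to be limited to treatment-emergent events. This stands as an objection to certainty. It does not remove the gap, because the text leaves the choice open and its literal reading is the unfavourable one.

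The evidence on how common baseline scale is remains thin. The description of AKs as scaly is general, exclusion criterion 2 removes hyperkeratotic and hypertrophic lesions, and nothing in the documents shows how often erythema or crusting is present before dosing. This also stands: the mechanism is clear, its frequency is not.

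The other tables are only a partial substitute. The change-from-baseline LSR table is for the composite score, the maxima are absolute, and no listed table counts subjects whose grade for a single component rose above Day 1.

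**Conclusion.** The point holds as a gap in one descriptive safety table. As written, Table 4 and SAP Table 2-51 allow lesion-specific scale that predates dosing, and has not worsened, to be reported as an application-site event in either arm. That does not match the standard the SAP sets for treatment-emergent events.

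The likely effect is to overstate any-grade incidence and shrink its between-arm difference by the factor (1 − b). This assumes that b is similar in the two arms, that new or worse responses are independent of baseline grade, and that subjects with a baseline grade are counted. The size in this trial cannot be determined because b is not given; the range of 16 down to 4 points is an illustration for an assumed 20-point difference. The graded LSR tables and the SCC endpoint are unaffected. Severity is minor: a cheap improvement.

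**What to change.** In Protocol 10.10.6.3, and in a footnote to SAP Table 2-51, state that:

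- an LSR is converted to a preferred term only when a post-dose grade exceeds that subject's Day 1 pre-dose grade for the same component;
- the Day 1 pre-dose assessment is itself excluded from the conversion.

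Leave the grade-by-visit tables unchanged, so that the absolute grades, including those at Day 1, remain visible.

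The cost is a sentence or two of text and one programming condition. The Day 1 grade is already collected, and no trial procedure changes. The downside is that reported LSR event percentages come out lower than under the any-grade rule, so the footnote should make the definition plain to anyone comparing them with any-grade figures.
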